3.5.2. Clinical Laboratory Assessments

Clinical laboratory assessments will be performed as described in the protocol.

To determine if there are any clinically significant laboratory abnormalities, the haematological, clinical chemistry (serum) and urinalysis safety tests will be assessed against the criteria specified in the sponsor reporting standards. The assessment will not take into account whether each participant's baseline test result, the measurement on Day -1, is within or outside the laboratory reference range for the particular laboratory parameter.

3.5.3. Vital Signs

Blood pressure and pulse rate will be measured as described in the protocol. The baseline measurement is the predose measurement on Day 1. Changes from baseline will be defined as the change between the postdose measurement on Day 2 and the baseline measurement.

3.5.4. Electrocardiograms

Single 12-lead ECGs will be performed as described in the protocol. The HR, PR, QT, QTcF, and QRS intervals will be captured.

The baseline measurement is the predose measurement on Day 1. Changes from baseline will be defined as the change between the postdose measurement on Day 2 and the baseline measurement. Change from baseline in QT interval, heart rate, QTcF interval, PR interval, and QRS complex will be determined.

4. ANALYSIS SETS (POPULATIONS FOR ANALYSIS)

Data for all participants will be assessed to determine if participants meet the criteria for inclusion in each analysis population prior to unblinding and releasing the database and classifications will be documented per standard operating procedures.

Population	Description	Applicable Analysis
Enrolled	“Enrolled” means a participant’s agreement to participate in a clinical study following completion of the informed consent process and randomization to study intervention. A participant will be considered enrolled if the informed consent is not withdrawn prior to participating in any study activity after screening. Potential participants who are screened for the purpose of determining eligibility for the study, but do not participate in the study, are not considered enrolled, unless otherwise specified by the protocol.	
Evaluable analysis set	All participants who take at least 1 dose of study intervention and provide at least 1 corresponding assessment to the Palatability Questionnaire.	Primary Endpoint
Safety analysis set	All participants randomly assigned to study intervention and who take at least 1 dose of study intervention. Participants will be analyzed according to the product they actually received.	Secondary Endpoint

5. GENERAL METHODOLOGY AND CONVENTIONS

5.1. Hypotheses and Decision Rules

No statistical hypothesis will be tested in this study.

5.2. General Methods

Descriptive analyses will be performed, and some measures will be summarized using graphical representations

The analyses related to the primary and secondary endpoints will be based on the appropriate population for analysis (see [Section 4](#)).

Unless otherwise stated, all summaries and plots will be presented by treatment group. The following treatment group labels (or similar) will be used:

- Treatment A: **CCI** mg/mL Sisunatovir **CCI**

- Treatment B: **CCI** mg/mL Sisunatovir, **CCI**
- Treatment C: **CCI**
- Treatment D: **CCI** mg/mL Sisunatovir and **CCI**
- Treatment E: **CCI** mg/mL Sisunatovir and **CCI**
- Treatment F: **CCI** mg/mL Sisunatovir, **CCI**

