3. OBJECTIVES AND ENDPOINTS

Objectives	Endpoints
Primary: 
To assess the palatability attributes of sisunatovir in different formulations	Primary: 
Palatability Assessment Questionnaire Scoring Metrics: mouth feel, bitterness, sweetness, sourness, saltiness, tongue/mouth burn, overall liking.
Secondary: 
To assess safety and tolerability following oral administration of each sisunatovir formulations	Secondary: 
Assessment of TEAEs, clinical laboratory abnormalities and vital signs.

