4. STUDY DESIGN

4.1. Overall Design

This is a single-blind, randomized, multi-period study in healthy male and/or female adult participants. Approximately 12 participants will assess the palatability attributes of a total of 6 formulations (Formulations A to F) over 2 days in a crossover manner. There will be a maximum of 4 periods each day, and one formulation will be administered at each period for tasting in a blinded fashion, except on Day 2 where there will be one period with no administration. A minimum of 3 participants from each gender is required.

All participants will be discharged on Day 2 after completion of all required assessments. If the participant accidentally ingests the taste sample containing the active ingredient, he/she will not be permitted to continue evaluating any further taste samples and will be withdrawn from the study.

The total planned duration of participation, from the Screening visit to the Follow-up contact, is approximately 5 to 8 weeks. The study consists of an initial screening period of up to 28 days prior to the first administration of study intervention, admission to the CRU on Day -1 and planned discharge on Day 2, following completion of assessments per **SoA**, and a follow-up contact that will occur 28-35 days after the final palatability assessment of PF-07923568.

In the event where the participant accidentally ingests the taste sample containing the active ingredient, he/she will not be permitted to continue evaluating any further taste samples and will be withdrawn from the study.

Participants who discontinue from the study may be replaced at the sponsor's discretion. The replacement participant will receive the same treatment sequences as the participant who discontinued.

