4.2. Scientific Rationale for Study Design

To minimize potential bias in the assessment of palatability by participants, this study will be single-blinded. A crossover design is planned hence allowing for within-participant comparison of the palatability scores, and the administration of a control formulation (CC1 mg/mL sisunatovir CCI) will be administered on each day of the assessment to control for potential differences between days. Bitrex serves as positive control to confirm if participants can taste bitterness. Additionally, it may provide bridging benchmark to compare against other marketed products as well as to assist the formulation of placebo for pediatric studies to have comparable bitterness levels if present.

The palatability of sisunatovir will be assessed to aid in development of pediatric formulations. Palatability will be assessed by all participants in a total of 8 periods with a minimum of 1 hour between each period, which is based on the typical washout of an hour used for palatability assessments. The formulation will be swirled in the mouth and spat out since it is not necessary to consume the study intervention to assess palatability. API combined with flavor, sweetener or a combination of both will be assessed to understand which excipients improve palatability and justify their inclusion in the pediatric formulation.

Due to the potential effect of smoking on taste sensitivity, participants who smoke or use tobacco/nicotine containing products are excluded from this study. Participants with conditions that affect ability to taste (eg, dysgeusia, respiratory infection, cold, etc) will also be excluded.

As this is healthy participant study, the use of concomitant medications in this study is expected to be minimal. Nevertheless, according to the DDI risk assessment for sisunatovir as described in Sections 2.2.2 and 2.2.4, sisunatovir is a moderate inhibitor of CYP3A4 and is projected to be a weak inhibitor of CYP2B6. For this reason sensitive and narrow TI CYP3A4 substrates and sensitive and narrow TI CYP2B6 substrates are prohibited in this study. Since sisunatovir is a P-gp and CYP3A4 substrate, strong and moderate CYP3A4 and P-gp inhibitors or inducers are prohibited. Lastly, due to risk of MATE1 and OCT1 inhibition, sensitive substrates of these transporters are prohibited. Use of specific prohibited prior/concomitant therapies are outlined in [Appendix 8](#).

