3.5.1. Adverse Events

Any adverse events occurring following start of treatment will be considered as treatment-emergent adverse events (TEAE). If an AE starts on the same day as the first dose date, it will be considered treatment-emergent unless the CRF data indicates otherwise via explicitly recording time for AE onset which has occurred before the first treatment dosing. Events that occur during follow-up within the lag time of up to 28-35 days after the last dose of study intervention will be counted as treatment-emergent and attributed to the last treatment taken. Events that occur during the washout period between treatments will be counted as treatment-emergent and attributed to the previous treatment taken. The time period for collecting AEs (“active collection period”) for each participant begins from the time the participant provides informed consent. The algorithm will not consider any events that started prior to the first dose date.

A 3-tier approach for summarizing adverse events (AEs) will not be used due to the low number of participants planned to be recruited.

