6.5.1. Adverse Events

Adverse events will be reported in accordance with the sponsor reporting standards.

Participant discontinuations due to adverse events will be detailed by treatment, where appropriate. Data will be reported in accordance with the sponsor reporting standards.

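### Under the SAP's default layout, control A's adverse-event column pools two tastings per participant against one for each of B to F; split A by day and print the tasting counts

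*SAP*

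**What the plan says.** Protocol 4.1 sets the size and scope: "Approximately 12 participants will assess the palatability attributes of a total of 6 formulations (Formulations A to F) over 2 days". Protocol 4.2 explains that the control formulation "will be administered on each day of the assessment to control for potential differences between days". In the sample scheme (Protocol Table 1, SAP Figure 1), each of the four sequences contains A once on Day 1 and once on Day 2, and B, C, D, E and F once each.

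The secondary objective is framed per formulation: "To assess safety and tolerability following oral administration of each sisunatovir formulations".

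The SAP text that governs the AE tables is as follows.
- **SAP 5.2:** "Unless otherwise stated, all summaries and plots will be presented by treatment group". Six labels follow, one of them for A, with the proviso that similar labels may be used.
- **SAP 5.2.2:** categorical data are reported as numbers and percentages of participants.
- **SAP 3.5.1:** "Events that occur during the washout period between treatments will be counted as treatment-emergent and attributed to the previous treatment taken"; events in follow-up "will be counted as treatment-emergent and attributed to the last treatment taken".
- **SAP 6.5.1:** "Adverse events will be reported in accordance with the sponsor reporting standards", and "Participant discontinuations due to adverse events will be detailed by treatment, where appropriate".
- **SAP 6.4.3:** exposure is listed only.

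By contrast, SAP 6.1 summarizes the palatability scores by session as well as by time point and treatment.

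**The concern.** A participant counts as having an AE on A if an event follows either of two tastings, but as having an AE on B only if one follows a single tasting. Both columns would show the same denominator of 12. If all formulations were equally well tolerated, A would still tend to show more affected participants, and nothing in the AE table would tell the reader that exposure was 2:1.

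This matters because the by-formulation AE table is the output that answers the secondary objective, and A is the formulation repeated as a control. A reader who sets B to F beside A would see them in a somewhat better light for a reason unrelated to the excipients. No test or model is planned for AEs, so the raw columns are all the reader has.

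**Working it through.** **The plan's own figures.** The documents state no AE rate, event count or power. The only sample-size figures are the palatability half-widths in Protocol 9.5. They reproduce from t(0.95, 11) × SD/√12 × √(χ²(0.80, 11)/11). For bitterness this gives 10.76 against the stated 10.8, and for mouth feel 15.55 against 15.5. They do not bear on AEs.

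**Tastings per column.** There are four sequences of 3 participants, all assumed to complete.
- A: 4 × 3 × 2 = 24.
- B, C, D, E and F: 4 × 3 × 1 = 12 each.
- Total: 24 + 5 × 12 = 84. A has 24/84 = 29% and each other formulation 12/84 = 14%.

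**Participant incidence with equal, independent risk p per tasting.** For A it is 1 − (1 − p)²; for any other formulation it is p. The ratio is 2 − p, and the expected gap among 12 participants is 12p(1 − p). The values of p are assumptions.

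| p per tasting | A | Other | Ratio | Expected participants of 12, A v other | Gap |
|---|---|---|---|---|---|
| 1% | 1.99% | 1% | 1.99 | 0.24 v 0.12 | 0.12 |
| 2% | 3.96% | 2% | 1.98 | 0.48 v 0.24 | 0.24 |
| 5% | 9.75% | 5% | 1.95 | 1.17 v 0.60 | 0.57 |
| 10% | 19% | 10% | 1.90 | 2.28 v 1.20 | 1.08 |
| 20% | 36% | 20% | 1.80 | 4.32 v 2.40 | 1.92 |

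The higher rows are demanding. Over seven tastings, 1 − (1 − p)⁷ implies that 30%, 52% and 79% of participants have an event at p = 5%, 10% and 20%.

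**Same person reacting both times.** With correlation ρ between a participant's two tastings of A, the ratio is 2 − p − ρ(1 − p). At p = 5%:
- ρ = 0.3: 1.95 − 0.285 = 1.67 (rounded).
- ρ = 0.6: 1.95 − 0.57 = 1.38.

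**Effect of splitting A by day.** Each A column then has 12 tastings, as B to F do, and the tasting-driven ratio is 1.

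**What the split leaves.** The last products tasted on Day 2 in the four sequences are F, A, A and E. Under the last-treatment rule in SAP 3.5.1, events in the 28-35 day follow-up go to A for 6 of 12 participants, to E for 3, to F for 3, and to B, C or D for none. A Day 2 would still carry twice the follow-up attribution of E or F. The Day 1 columns do not have this problem: the sequences end Day 1 with C, D, A and B, so overnight attribution is even.

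**The case against.** **The layout is inferred.** A reader might infer that the SAP definitely places all of A's AEs in one column. The documents do not go that far. SAP 6.5.1 defers to sponsor reporting standards that are not reproduced, and the SAP 5.2 labels are open to variation. What stands is that the only presentation rule in the SAP leads to one A column, and nothing in it says otherwise for AEs.

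**Doubling is a ceiling.** A reader might also infer that A's incidence will be about twice the others. That needs equal, independent risk and low p; with correlated reactions the factor falls well below 2. Protocol 2.2.4 describes related events in adults as low in occurrence, and Protocol 4.3 expects no appreciable absorption from swirling and spitting. Rates of 5% or more per tasting may therefore be too high, and at 1% to 2% the gap is 0.12 to 0.24 of a participant. This objection stands in full as to size.

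**A is a control for palatability.** Protocol 4.2 links the crossover to within-participant comparison of palatability scores. No section plans an AE comparison against A, and no hypothesis is tested. Pooling both tastings is a legitimate description of all safety data on A. That is why a pooled column may stay. It does not remove the need to show the exposure behind each column when the objective is per formulation.

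**Readers can see the scheme.** Both documents print it, and exposure is listed. A careful reader could work out the 2:1 ratio, but the table should not depend on that.

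**Conclusion.** The point holds as a minor to moderate reporting issue. If the SAP's default is followed, A's AE column rests on 24 tastings and each other column on 12. With equal per-tasting risk, A's participant incidence is inflated by a factor of up to 2 − p. The tasting counts follow from the scheme. The factor depends on assumed rates, on how strongly a participant's two reactions to A are correlated, and on a column layout inferred from SAP 5.2.

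The documents do not support reading this as a biased test or as a planned safety comparison with A. The effect is limited to how the by-formulation safety table reads. Nor do they show what Treatment C is, since its description is redacted, so no conclusion should treat C as an excipient formulation to be set against A.

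**What to change.** Amend SAP 5.2 and 6.5.1 as follows.

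1. For AEs and AE discontinuations, show A in two columns, one for Day 1 and one for Day 2. A pooled A column may be kept as well.
2. Print the number of tastings actually given in every column header, so that withdrawals before Day 2 are also visible.
3. Read the Day 1 formulations (B, C, D) beside A Day 1 and the Day 2 formulations (E, F) beside A Day 2, without assuming what C is.
4. Show events with onset in the 28-35 day follow-up separately from the tasting-day columns, and state the cut-off between the two. Without this step, A Day 2 keeps twice the follow-up attribution of E or F in the sample scheme.

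The cost is a few lines of SAP text and a slightly wider table. No new data and no change to the trial's conduct are needed.

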5.2.1. Analyses for Continuous Endpoints

For continuous variables; the data will be summarized using number of participants, arithmetic mean, standard deviation (SD), median and range (minimum and maximum) in accordance with the sponsor reporting standards.

5.2.2. Analyses for Binary/Categorical Endpoints

For binary or categorical variables; number of participants, numbers and percentages of participants meeting the categorical criteria will be presented in accordance with the sponsor reporting standards.

5.3. Methods to Manage Missing Data

For the analysis of safety endpoints, the sponsor data standard rules for imputation will be applied.

6. ANALYSES AND SUMMARIES.

6.1. Primary Endpoint(s)

The sensory attributes (mouth feel, bitterness, sweetness, sourness, saltiness, tongue/mouth burn, overall liking) from the palatability questionnaires ([Appendix 2](#)) will be listed and descriptively summarized by session, time point, and treatment, if appropriate. Summary statistics (mean and 90% CI) will be calculated for the various questions. Radar plots for each of 4 time points, summarizing all attributes will be generated. Boxplots of each attribute will be plotted against the time points. Any additional feedback data as collected by the palatability questionnaire will be listed.

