9.3.2. Primary Endpoint(s) Analysis

The data collected for palatability assessment using the sponsor-provided palatability questionnaire will be numerically derived by measuring length (using a scale with gradations of at least 0.1 cm) of the “x” marked by the participant relative to the “good trait”. For palatability assessment, the data used in the analysis will be transcribed and rescaled to a score from 0 to 100 from the raw measurements on the questionnaire. The palatability attributes (mouth feel, bitterness, sweetness, sourness, saltiness, tongue/mouth burn, overall liking) from the palatability questionnaire ([Appendix 9](#)) will be listed and descriptively summarized by session and time points using evaluable analysis set. Appropriate plots may be generated, such as radar plots and boxplots.

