9.5. Sample Size Determination

A sufficient number of participants will be screened to achieve 12 participants randomized to study interventions. The sample size is empirically selected and is not based on statistical power calculation.

With a sample size of 12 participants, the expected half-width of 2-sided 90% CIs of the estimated mean score for each palatability assessment with 80% probability coverage are shown below. The SDs were obtained from the Bitrex group of study B7981021.

Palatability assessment	SD	Half-Width of the 90% CI with 80% coverage
Bitterness	18.0	10.8
Mouth Feel	26.0	15.5
Overall Liking	22.7	13.6
Saltiness	24.4	14.6
Sourness	23.5	14.0
Tongue / Mouth Burn	17.7	10.6

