2.3. Study Design

This is a single-blind, randomized, multi-period study in healthy male and/or female adult participants. Approximately 12 participants will assess the palatability attributes of a total of

6 formulations (Formulations A to F) over 2 days in a crossover manner. There will be a maximum of 4 periods each day, and one formulation will be administered at each period for tasting in a blinding fashion, except on Day 2 where there will be one period with no administration. A minimum of 3 participants from each gender is required.

All participants will be discharged on Day 2 after completion of all required assessments. If the participant accidentally ingests the taste sample containing the active ingredient, he/she will not be permitted to continue evaluating any further taste samples and will be withdrawn from the study.

Participants who discontinue from the study may be replaced at the sponsor's discretion. The replacement participant will receive the same treatment sequences as the participant who discontinued.

The study sample dosing scheme is shown below in Figure 1.

Figure 1. Sample Dosing Scheme

	Session 1 (Day 1)				Session 2 (Day 2)			
	Period 1	Period 2	Period 3	Period 4	Period 5	Period 6	Period 7	Period 8
N=3	A	B	D	C	A	E	No	F
N=3	B	C	A	D	E	F	A	No
N=3	C	D	B	A	F	No	E	A
N=3	D	A	C	B	No	A	F	E

Treatment A: CCI mg/mL Sisunatovir CCI
 Treatment B: CCI mg/mL Sisunatovir, CCI

Treatment C: CCI

Treatment D: CCI mg/mL Sisunatovir and CCI

Treatment E: CCI mg/mL Sisunatovir and CCI

Treatment F: CCI mg/mL Sisunatovir, CCI

No: No administration and indicated as 'X' in randomization

Note CCI

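### The committed primary analysis gives no interval for any difference between formulations, and E/F against B/C/D read from the reported means carries any day shift

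*SAP*

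**What the plan says.** Protocol 4.2 gives comparative reasons for the design. On the crossover: "A crossover design is planned hence allowing for within-participant comparison of the palatability scores". On the control formulation: it "will be administered on each day of the assessment to control for potential differences between days". A is the only formulation given on both days in the sample scheme, so A is that control. On the purpose: the drug combined with flavor, sweetener or both will be "assessed to understand which excipients improve palatability and justify their inclusion in the pediatric formulation".

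The analysis sections are not comparative:

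- Protocol 9.3.2: the attributes "will be listed and descriptively summarized by session and time points using evaluable analysis set".
- Protocol 9.5: precision is given as "the expected half-width of 2-sided 90% CIs of the estimated mean score for each palatability assessment", that is, for single means.
- SAP 6.1: summaries by session, time point and treatment, with a qualifier that this grouping applies where appropriate. Then: "Summary statistics (mean and 90% CI) will be calculated for the various questions". Radar plots and boxplots follow, with no session named.
- SAP 5.2: "Unless otherwise stated, all summaries and plots will be presented by treatment group". The label list has one entry for A.
- SAP 6.1.1: a mixed model with treatment, sequence, time point and period as fixed effects. It is conditional on the data and worded as optional. It combines the time points and does not say whether its estimates are means or differences.

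Protocol Table 1 and SAP Figure 1 show the same sample scheme. In all four sequences A is tasted on both days, B, C and D only on Day 1, and E and F only on Day 2.

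**The concern.** The question is which excipients improve palatability, and that is a question about differences. The committed output has an interval for each mean and none for any difference. A reader who judges a difference from two marginal intervals ignores the pairing that the crossover was chosen to provide.

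The second problem is the day. Setting the Day 2 means of E and F beside the Day 1 means of B, C and D mixes formulation with day. The repeated A exists to separate the two, but no committed analysis uses it for that. Because the plots name no session and are laid out by treatment, they may put E/F beside B/C/D and pool the two A sessions.

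**Working it through.** **Inputs.** n = 12 and SD 18.0 for bitterness and 22.7 for overall liking (protocol 9.5; the SDs come from the Bitrex group of another study). Day allocation from protocol Table 1. The within-participant correlation r is not in the documents, so I assume 0, 0.3, 0.5 and 0.7, and equal SD for all formulations.

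**1. The plan's own figures.** Half-width = t(0.95, 11) × SD / √12 × √(χ²(0.80, 11)/11) = SD × 0.5184 × 1.1533 = 0.5979 × SD. This gives 10.76 for bitterness, 15.55 mouth feel, 13.57 overall liking, 14.59 saltiness, 14.05 sourness and 10.58 burn. The protocol states 10.8, 15.5, 13.6, 14.6, 14.0 and 10.6. They agree to within 0.1 and are precision for single means.

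**2. Precision of a difference** (90% CI, without the 80% assurance factor).

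- Two means read as independent: t(0.95, 22) × SD × √(2/12)
- Same-day paired difference: t(0.95, 11) × SD × √(2(1−r)/12)
- Cross-day, (E − A on Day 2) − (B − A on Day 1): t(0.95, 11) × SD × √(4(1−r)/12)

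For SD 18.0 the first is 12.6. The others, with the change against 12.6, are:

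| r | Same-day paired | Cross-day via A |
|---|---|---|
| 0 | 13.2 (5% wider) | 18.7 (48% wider) |
| 0.3 | 11.0 (13% narrower) | 15.6 (24% wider) |
| 0.5 | 9.3 (26% narrower) | 13.2 (5% wider) |
| 0.7 | 7.2 (43% narrower) | 10.2 (19% narrower) |

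Break-even r is about 0.09 for the same-day contrast and 0.54 for the cross-day contrast.

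With the protocol's 80% assurance (factor √(χ²(0.80, df)/df), df 22 or 11), the independent reading gives 14.1. Same-day gives 15.2, 12.7, 10.8 and 8.3; cross-day gives 21.5, 18.0, 15.2 and 11.8. Break-even r is then about 0.15 and 0.57.

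For overall liking without assurance, the independent reading gives 15.9. At r = 0.3, 0.5 and 0.7, same-day gives 13.9, 11.8 and 9.1, and cross-day gives 19.7, 16.6 and 12.9.

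**3. Day shift.** Suppose Day 2 adds d points to every score.

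- The E and F means contain d and the B, C and D means do not, so every raw E/F minus B/C/D difference moves by d.
- An A mean pooled over both days contains d/2. Differences from it move by −d/2 for B, C and D and by +d/2 for E and F.
- Contrasts within B/C/D, and E against F, do not move.

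**4. Whether the design supports the contrasts.** In the sample scheme A, B, C and D each appear once in each of Periods 1–4, and A, E and F once in each of Periods 5–8. With complete data, mean same-session differences from A are therefore free of additive period effects. A model with participant, period and treatment at one time point has 84 records, full rank (24 of 24) and 60 residual degrees of freedom. The standard error is 0.408 σ_w for same-day or versus-A contrasts and 0.577 σ_w for E/F against B/C/D, where σ_w is the within-participant SD. Every contrast of interest can be estimated.

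**The case against.** The study is descriptive. It has no hypothesis and no estimand, an empirical sample size, and an objective worded as assessing attributes. SAP 6.1 delivers what protocol 9.3.2 describes. The comparative language sits in the design rationale and promises no interval. That stands, and it limits the consequence: no test is wrong. But the plan already reports 90% CIs, and attaching them to differences serves its own rationale.

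The 6.1.1 model has a period term that would absorb an additive day shift. That also stands, and it shows the fix is feasible. The model remains optional, pools time points and names no contrast.

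Participant-level scores will be listed, so a reader could compute every paired difference. With complete data, subtracting the by-session means even gives the same point estimate. The interval, however, cannot be had from the summary tables, and listings leave the reader to do the analysis.

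The plot concern is about silence, not a stated plan to pool, and the note under the scheme is redacted. Treatment C is the only one whose visible label does not name sisunatovir, so it may be the Bitrex control. If so, its contrasts do not bear on excipients and the useful set is smaller. Finally, the layout is labeled a sample scheme, though both documents carry it and neither shows another.

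**Conclusion.** The concern holds. The committed analysis has no interval for any formulation difference, and raw E/F against B/C/D differences carry any day shift in full.

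For same-day contrasts the loss is a valid and usually narrower interval: 13% to 43% narrower at r from 0.3 to 0.7. For cross-day contrasts the loss is protection against day bias; the proper interval is wider than the independent reading unless r exceeds about 0.54.

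These sizes rest on an assumed r common to all pairs, a borrowed SD taken as equal across formulations, and the sample scheme. The day-shift result assumes a shift that is additive and equal for all formulations, which is uncertain on a bounded 0–100 scale. The documents give no figure for the shift itself. This should be changed, but it does not invalidate the study.

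**What to change.** In SAP 6.1, commit to:

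1. Each participant's difference from their own same-session A, per attribute and time point, with mean and 90% t-interval for B, C, D, E and F.
2. A Day 2 minus A Day 1, with 90% CI, as the day-shift check.
3. For E/F against B/C/D, the difference of the differences in item 1, with 90% CI.

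Alternatively, commit to the 6.1.1 model fitted separately at each time point, with these contrasts named. In either case state that the intervals are descriptive and unadjusted, show A separately by session in the plots, and name in advance the attribute and time point for the main tables.

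The cost is wording and tables; no new data are needed. The full set is 7 × 4 × 5 = 140 differences from A, 7 × 4 = 28 day checks and up to 7 × 4 × 6 = 168 cross-day contrasts. If C is not a candidate formulation, the first and last fall to 7 × 4 × 4 = 112 each. That is many intervals from 12 participants, and the cross-day ones may be wide, so they should be read descriptively.
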